2.4 Endpoints

The primary endpoint is pathological complete response (pCR) as defined by no evidence of tumor cells in the final surgical specimen
The secondary endpoints are ORR per RECIST 1.1 criteria, recurrence disease-free and incidence of AEs

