4.0 TREATMENT PLAN

4.1 Treatment Dosage and Administration

- 4.1.1 Abemaciclib will be administered orally at the dose of 150 mg twice daily. Fulvestrant will be administered intramuscularly at an initial loading dose of 500mg on days 1 and 15 of the first cycle and then 500 mg intramuscularly every first day of each subsequent cycle. One cycle is 28 days.

REGIMENT DESCRIPTION				
Agent	Dose	Route	Schedule	Cycle Length

CONFIDENTIAL

This material is the property of the [UC Irvine Chao Family Comprehensive Cancer Center](#). Do not disclose or use except as authorized in writing by the study sponsor.

Abemaciclib	150 mg	Oral (PO)	BID	4 weeks (28 days)
Fulvestrant	500 mg	IM	C1D1, C1D15, and D1 of each subsequent cycle	

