4.1.2 Supportive Care Guidelines

Necessary supportive measures for optimal medical care will be given throughout the study including antidiarrheal, blood components etc. Additional care will be administered as indicated by the treating physician and the subject's medical need. All the concomitant medications and supportive therapy administered during the 30 days prior to the first dose until 30 days after the last dose must be recorded in OnCore eCRF.

4.2 **Toxicities and Dosing Delays/Dose Modifications**

Any patient who receives treatment on this protocol will be evaluable for toxicity. Each patient will be assessed for the development of toxicity according to the Time and Events table (Section 5.4). Toxicity will be assessed according to the NCI Common Toxicity Criteria for Adverse Events (CTCAE), version 5.0. Dose adjustments should be made according to the system showing the greatest degree of toxicity.

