5.3 Procedures During Treatment

5.3.1 Prior to Each Treatment Cycle

- Physical exam, vital signs
- Hematology
- Serum chemistries
- Adverse events
- Study drug accountability
- Review previous and current concomitant medications

Site must maintain an accurate and timely record of dispensing of study drug to subject, and receipt of all study drug and pill diaries.

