5.4 Follow-up Procedures

Patients will be followed every 6 (+/- 14 days) months after surgery until patient comes off study due to study completion at 5 years, death, or withdrawal, whichever comes first

- Blood collection for ctDNA

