5.5 Time and Events Table

If baseline evaluations are conducted within 1 week prior to administration of protocol therapy, those assessments do not need to be repeated. Scans must be done \leq 4 weeks prior to the start of therapy. In the event that the patient's condition is deteriorating, laboratory evaluations should be repeated within 48 hours prior to initiation of the next cycle of therapy.

	Baseline/Screening	Treatment Phase		Post-discontinuation		
	-28 to -1 days	Cycle 1	Subsequent cycles	End of Treatment	Surgery	Follow-up

CONFIDENTIAL

This material is the property of the [UC Irvine Chao Family Comprehensive Cancer Center](#). Do not disclose or use except as authorized in writing by the study sponsor.

		D1 (-3d)	D15 (±3d)	D1 (-3d)	Within 30 days of last dose prior to surgery		Every 6 months (±14d)
Assessment							
Informed Consent	X						
History and PE	X	X		X	X		
Vital Signs	X	X	X	X	X		
Baseline medical and oncology history	X						
Concomitant Medications	X	X		X	X		
ECOG Performance Status	X	X		X	X		X
Adverse Events		X		X	X		
Tumor Measurements	X						
CT CAP or CT chest/MRI Abd/Pelvis ¹	X						
MRI Breast	X			X Every 12 weeks (±7d) after first dose until maximum response or progression, whichever occurs first			
CBC w/diff	X	X	X	X	X		
CMP	X	X	X	X	X		
Postmenopausal Confirmation	X						
ctDNA (correlative study)	X			X ²			X
Biopsy ³					X		
Tissue Submission	X				X	X	
Administer Abemaciclib		X	X	X			
Administer Fulvestrant		X	X	X			
Study Drug Accountability				X	X		

¹ CT Chest, abdomen and pelvis with contrast or CT chest/MRI Abdomen, Pelvis is required at screening to rule out metastasis

² Every 3 months during treatment

CONFIDENTIAL

This material is the property of the [UC Irvine Chao Family Comprehensive Cancer Center](#). Do not disclose or use except as authorized in writing by the study sponsor.

³ A fresh biopsy at time of progression is mandatory if clinically feasible.

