8.3 Agent Accountability

Accountability for the study drug at the study center is the responsibility of the Investigator. The Investigator will ensure that the study drug is used only in accordance with this protocol. Where allowed, the Investigator may choose to assign drug accountability responsibilities to a pharmacist or other appropriate individual.

The Investigator or delegate will maintain accurate drug accountability records indicating the drug's delivery date to the site, inventory at the study center, use by each patient, and destruction.

These records will adequately document that the patients were provided the doses as specified in the protocol and should reconcile all study drug received from Eli Lilly Pharmaceuticals.

Study drug must not be used for any purpose other than the present study. Study drug that has been dispensed to a patient and returned unused must not be redispensed to a different patient.

Patients will receive instructions for home administration of Abemaciclib according to the regimen description above. Abemaciclib is to be taken twice a day. If doses of Abemaciclib are missed or held, the patient should not make up for the missed doses. Patients will be given a study medication diary to complete at home for Abemaciclib. Compliance with the dosing regimen will be assessed based on completion of the drug diary and return of unused drug (or empty bottles).

IMP Destruction

IMP will be destroyed by the sites according to their institutional policies. Documentation of IMP destruction should be made available to Eli Lilly Pharmaceuticals at the end of the study.

IMP Returns

CONFIDENTIAL

This material is the property of the [UC Irvine Chao Family Comprehensive Cancer Center](#). Do not disclose or use except as authorized in writing by the study sponsor.

Eli Lilly Pharmaceuticals will not accept returned IMP

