Table X1 presents sample size of Simon's two-stage design. Where n is the total number of subjects, n₁ is the number of subjects accrued during stage 1, if r₁ or fewer responses are observed during stage 1, the trial is stopped early for futility. If r₂ or fewer responses are observed by the end of stage two, then no further investigation of the drug is warranted, EN₀ is the expected sample size for the trial when response rate is p₀ and p₀ and p₁ are the response probabilities under the null and under the alternative hypothesis. Thus, the null hypothesis that the true response rate is 10% will be tested against a one-sided alternative. In the first stage, 10 patients will be accrued. If there are one or fewer responses in these 10 patients, the study will be stopped. Otherwise, 19 additional patients will be accrued for 29. The null hypothesis will be rejected if 6 or more responses are observed in 29 patients. This design will yield a type I error rate of 0.0471 and power of 80% when the true response rate is 0.3. Thus, we anticipate recruiting 29 evaluable participants with at least 10 in stage 1. (Simon 1984, Jung et al 2004) (16, 17). Given the sample size of 30 participants, power in the statistical design will be low for the secondary and exploratory endpoints. Efficacy of the study as measured by estimating the objective response rate in the breast and/or the axillary lymph nodes or determining if the combination of Abemaciclib and Fulvestrant increases the percentage of patients who undergo breast conserving surgery will be measured by constructing 95% CI. We plan to use survival analysis methods such as Kaplan- Meier estimates of survival probability for univariate analysis and log rank tests in order to test for differences among different patient characteristics such as age group for recurrence or disease-free survival. For multivariate analysis in order to examine survival adjusted for a number of covariates we plan to use the Cox proportional hazards model. In order to examine the safety and toxicity which will be determined by the incidence of treatment-emergent, treatment-related adverse events (TRAEs), and serious adverse events (SAE) we plan to monitor side effects and adherence to the protocol throughout the duration of the study. Interim analyses will be performed to assess the presence of side effects. Contingency tables will be constructed to compare the proportion of patients with side effects by study characteristics as age, race ethnicity and other clinical and epidemiologic characteristics. Distributions of all data items will be generated and examined for the presence of outliers, in order to assess the general form of the distributions, and to compute measures of central tendency and variability. Trellis graphics will be used for data display including histograms, boxplots, and Q-Q normal plots. In addition, we plan to examine if genomic analysis of patient matched breast tissue samples and serial mutational tracking of circulating tumor DNA can identify new mechanisms of endocrine resistance and how

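### Both pill diaries stop at Day 22 of a 28-day cycle, and the laboratory schedule, the diary's symptom instruction and the ciprofloxacin class each differ between sections and need reconciling

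*Combined protocol and SAP*

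**What the plan says.** **Diary.** Section 4.1.1: "One cycle is 28 days", with abemaciclib taken twice daily and no off-days in the regimen table. Section 8.3 names two sources for compliance: "Compliance with the dosing regimen will be assessed based on completion of the drug diary and return of unused drug (or empty bottles"). Section 5.3.1 adds: "Site must maintain an accurate and timely record of dispensing of study drug to subject, and receipt of all study drug and pill diaries". In Appendix D, the last day in the Cycle 1 diary is Day 22, and so is the last day in the diary for Cycle 2 onward.

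**Safety laboratories.** The hematologic and hepatic guidelines in Section 4.2.1 list blood counts and ALT before treatment, two-weekly through month two, then monthly for two months and as clinically indicated. Section 4.2 says: "Each patient will be assessed for the development of toxicity according to the Time and Events table (Section 5.4"). That number is wrong: the heading there is "5.4 Follow-up Procedures", and the table stands under "5.5 Time and Events Table". The table has a Day 15 column in Cycle 1 only; later cycles show blood counts and the metabolic panel (which includes ALT, Section 5.1.12) on Day 1. Section 5.3.1 lists hematology and chemistries among the procedures before each cycle.

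**Symptoms.** Both diaries instruct the patient to leave out the dose and call the study team if symptoms of any kind occur. Section 4.2.1 requires no dose modification for Grade 1 diarrhea, or for Grade 1-2 events in its general non-hematologic table unless Grade 2 persists or recurs. At first loose stools it has the patient start an antidiarrheal and notify the investigator.

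**Ciprofloxacin.** Section 4.4 gives it as an example of a moderate CYP3A inhibitor; Appendix C lists it among the strong ones.

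**The concern.** These are conflicts between texts that different users may consult, so what happens to a patient can depend on which page is followed.

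1. The diary asks for dates, times and skipped doses, but gives nowhere to write them for the last six days of each cycle.
2. A site following the table, which Section 4.2 names for toxicity assessment, omits a safety draw that 4.2.1 lists. The dose rules in 4.2.1 turn on laboratory grades, including recurrent Grade 3 hematologic toxicity and persistent or recurrent Grade 2 ALT or AST elevation, so the timing of draws affects when those rules are triggered. Section 7.4 gives safety procedures missed at set time points as an example of a violation, and the documents do not settle whether an omitted Day 43 draw is one.
3. A patient may omit a dose in a situation where 4.2.1 requires no modification. Section 8.1 lists diarrhea and nausea as common side effects, so the situation is foreseeable.
4. Section 4.4 handles strong and moderate inhibitors differently, so the class label matters. The supportive-care text for diarrhea (within Section 4.4, numbered 4.3.2) mentions fluoroquinolones, so the question could arise in this trial.

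**Working it through.** The plan states no figure for any of these items, so there is none to reproduce.

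**Diary coverage.** Inputs: 28-day cycle and twice-daily dosing (4.1.1); last diary day 22 (Appendix D).
- Scheduled doses per cycle: 28 × 2 = 56.
- Doses with a row: 22 × 2 = 44, or 44/56 = 78.6%.
- Doses without a row: (28 − 22) × 2 = 12, or 12/56 = 21.4%.
- Over three cycles (3 × 28 = 84 days): 3 × 12 = 36 of 3 × 56 = 168 doses.

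Could the text extraction have cut the diaries short? Both templates stop on the same day with a complete final entry, and the next heading follows directly each time. A cut is unlikely, but the PDF pages should be checked.

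**Laboratory days.** Nominal days, no cycle delay, two months taken as eight weeks:

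| Source | Days |
|---|---|
| 4.2.1, two-weekly | 1, 15, 29, 43, 57 |
| Time and Events table | 1, 15, 29, 57 |
| 5.3.1, pre-cycle list | 1, 29, 57 |

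The table lacks Day 43 (Cycle 2 Day 15). Its gap from Cycle 2 Day 1 to Cycle 3 Day 1 is 57 − 29 = 28 days; 4.2.1 implies 43 − 29 = 14. The list in 5.3.1 shows neither Day 15 nor Day 43. After month two, Day 1 of each 28-day cycle is compatible with monthly draws, so the conflict is confined to the first two months.

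**Symptom instruction.** The diary's trigger is any symptom, with no grade threshold, and its action is to omit the dose and call. For Grade 1 diarrhea, 4.2.1 lists no dose modification. For Grade 2 diarrhea it suspends if the event has not settled to Grade 1 or less within 24 hours, or if it persists or recurs. For other non-hematologic events in its general table it acts on persistent or recurrent Grade 2 and on Grade 3-4. The documents give no symptom frequency or duration from which to estimate omitted doses.

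**Ciprofloxacin.** One drug, two class labels; no arithmetic applies.

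**Side check on the design.** With 10 then 19 patients, and rejection at 6 or more responses in 29, exact binomial sums give early stopping 0.7361, type I error 0.0471 and power 0.8051, as Section 10.2 states. Expected size under the null is 10 + (1 − 0.7361) × 19 = 15.0. None of these uses dosing or laboratory records.

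**The case against.** Several stronger readings are tempting, and the documents do not support them.

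- A reader might infer that compliance cannot be assessed after Day 22. It can be assessed in total: Section 8.3 also relies on returned drug, and the Time and Events table has drug accountability at each later Day 1 and at end of treatment. What is lost is dates and times. The 21.4% is a share of doses without a row, not of lost compliance data.
- A reader might cite Section 10.2, "we plan to monitor side effects and adherence to the protocol throughout the duration of the study", as a commitment to dose-adherence analysis. That sentence concerns safety and adherence to the protocol generally. Adherence is not an endpoint; Section 2.4 reads: "The secondary endpoints are ORR per RECIST 1.1 criteria, recurrence disease-free and incidence of AEs", after pCR as primary.
- A reader might count three rival laboratory calendars. Section 5.3.1 is a list of pre-cycle procedures and also leaves out other scheduled items, such as ECOG status and ctDNA. The real conflict is 4.2.1 against the table, one draw; 5.3.1 merely fails to show the Day 15 draw.
- A reader might apply the 3-day windows to get a wider gap. The result depends on whether windows run from the planned calendar or the actual previous cycle start, which is not stated. The nominal 28 against 14 days suffices.
- A reader might see the diary and 4.2.1 as irreconcilable. The diary may intend an interim hold until staff assess, which for diarrhea is set at 24 hours, and Section 4.2.2 permits holds within a cycle. That is plausible, but neither text says it.
- Appendix C calls itself guidance that does not preclude use, which limits the ciprofloxacin item. The mismatch in labels remains.

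The wrong section number in 4.2 is harmless in itself, because the table is cited by name.

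**Conclusion.** The point holds as a set of document conflicts to be corrected. In order of weight:

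1. Six of 28 days, 12 of 56 doses, have no dated row in any cycle, assuming the PDF pages match the extracted text.
2. One blood-count and ALT draw, at about Day 43, separates 4.2.1 from the table for each patient still on treatment then, assuming no cycle delay.
3. The diary's symptom instruction and the grade-based rules are unreconciled; the effect on exposure cannot be quantified from the documents.
4. One drug carries two class labels, a minor matter.

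This deserves correction because following the table drops a listed safety draw, and using the diary as printed leaves the dosing record incomplete by date. A reader might go further and infer harm to the primary result. The documents do not support that: neither the Simon decision rule nor the pCR assessment draws on these records.

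**What to change.** 1. After checking the PDF pages, give both diaries rows for all 28 days.
2. Reconcile Section 4.2.1, Section 5.3.1 and the Time and Events table to one blood-count and ALT schedule for the first two months, and correct the cross-reference in Section 4.2 from 5.4 to 5.5.
3. Reconcile the diary's symptom instruction with 4.2.1. If an interim hold pending staff assessment is meant, say so in both.
4. Classify ciprofloxacin the same way in Section 4.4 and Appendix C.

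For items 2 to 4 the sponsor's clinical team decides which text holds; this review takes no position.

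The cost is an amendment with IRB approval before implementation (Section 11.5) and reprinted diaries. If the two-weekly schedule is the one kept, add one draw per patient relative to the current table and possibly one visit, because the table has no Cycle 2 Day 15 visit.

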9.0 CORRELATIVE STUDY

Molecular analysis in the form of Next Generation Sequencing (NGS) will be performed on the treatment naïve archival breast tissue, on the breast tissue at the time of recurrence and on the surgical specimen. Blood will be collected as well for analysis of ctDNA before enrollment, every 3 months while on the treatment and then every 6 months (after definitive surgery) until the end of the study at five years. The molecular analysis by NGS will be done by Tempus using their standard platform.

Correlative Study Objective:

1. To determine if genomic analysis of patient matched breast tissue samples and serial mutational tracking of ctDNA can identify new mechanisms of endocrine resistance and the way Abemaciclib overcomes endocrine resistance
2. To determine the mechanism of response or resistance to Abemaciclib
3. To determine biomarkers related to the Rb pathway

Collection of tumor samples (archival, at time of recurrence, and from surgery) and ctDNA blood are mandatory.

10.0 STATISTICAL CONSIDERATIONS

Pathological response (pCR) is a tool to measure the efficacy of Neo-Adjuvant therapy. A complete pCR is defined as the absence of invasive cancer in the tumor and/or the axillary lymph node in the surgical pathology specimen after undergoing Neo-Adjuvant therapy. Chemotherapy can shrink HR- positive tumors and facilitate better surgical options, but is less likely to achieve a pathologic complete response (pCR) in HR-positive cancers, especially luminal A cancers, than for more proliferative histologies. Multiple metaanalysis have shown that pCR has prognostic implications even in patients with HR+ breast cancer. However, a limitation of using pCR to predict outcomes in patients with ER+ disease is that only 2 to 10 percent of patients with ER + disease achieve a pCR with NACT. In the post-menopausal setting, Aromatase Inhibitors are recommended over Tamoxifen as Neoadjuvant endocrine therapy based on clinical trials and meta-analysis. AIs resulted in higher clinical response rate (OR 1.69, 95% CI 1.36-2.10), radiologic response rate (OR 1.49, 95% CI 1.18-1.89), and BCS rate (OR 1.62, 95% CI 1.24-2.12) compared with tamoxifen (18).

Several trials have also investigated the role of endocrine therapy in combination with other targeted therapies. For example, in the randomized phase II UNICANCER-NEOPAL study, the combination of neoadjuvant palbociclib and letrozole resulted in slightly lower pCR rates compared with neoadjuvant third-generation chemotherapy, but the rates of clinical response and breast-conserving surgery were similar, with less frequent serious adverse events (19). Another study compared different doses of neoadjuvant fulvestrant (500 mg/month versus 250 mg/month) given for 16 weeks prior to surgery (20). Similar to what has been observed in the metastatic setting, the study demonstrated that the higher dose of fulvestrant was superior and had a greater antiproliferative effect. At week 16, tumor response rates were 22.9 and 20.6% for fulvestrant 500 and 250 mg, respectively, with considerable decline in all markers by both imaging and the ER/PR scoring method.

CONFIDENTIAL

This material is the property of the [UC Irvine Chao Family Comprehensive Cancer Center](#). Do not disclose or use except as authorized in writing by the study sponsor.

Several ongoing trials are investigating the role of combination therapy, including the combination of AIs with cyclin-dependent kinase (CDK) 4/6 inhibitors (NeoMONARCH), PI3K inhibitors (LORELEI), and dual endocrine therapy (ALTERNATE).

The NeoMONARCH study randomly assigned postmenopausal women with early stage HR+ breast cancer to Neoadjuvant therapy with Anastrozole, Abemaciclib or Anastrozole with Abemaciclib. The study met its primary endpoint by showing that Ki67 levels were significantly reduced in breast cancer cells from the 107 patients who received abemaciclib, either alone or in combination with anastrozole, compared with the 54 patients who received anastrozole only. Treatment with abemaciclib plus anastrozole led to a reduction in tumor size in most patients, as assessed by clinical and radiologic evaluation. Patients in this study received Abemaciclib only for two weeks. Therefore, extending Neo- Adjuvant Abemaciclib (beyond two weeks) as proposed in the current trial and combining it with high dose Fulvestrant is expected to achieve a higher response rate, greater anti-proliferative effect as measured by the Ki-67 index and perhaps improve Breast conservation surgery (21).

Similarly, the MONARCH 2 study compared the efficacy and safety of abemaciclib plus fulvestrant with fulvestrant alone in patients with advanced HR + breast cancer. Abemaciclib plus fulvestrant significantly extended PFS versus fulvestrant alone (median, 16.4 v 9.3 months; hazard ratio, 0.553; 95% CI, 0.449 to 0.681; $P < .001$). In patients with measurable disease, abemaciclib plus fulvestrant achieved an ORR of 48.1% (95% CI, 42.6% to 53.6%) compared with 21.3% (95% CI, 15.1% to 27.6 %) in the control arm (22).

The MONALEESA-3 study was a phase III study evaluated ribociclib plus fulvestrant in patients with hormone receptor-positive/human epidermal growth factor receptor 2-negative advanced breast cancer who were treatment naïve or had received up to one line of prior endocrine therapy in the advanced setting. Among patients with measurable disease, the overall response rate was 40.9% for the ribociclib plus fulvestrant arm and 28.7% for placebo plus fulvestrant (23).

The cohort in the proposed trial have had local recurrence while on adjuvant endocrine therapy. Hence, they are expected to have molecular evidence of endocrine resistance. Since Fulvestrant and CDK 4/6 inhibition have been shown to benefit patient with endocrine resistance, we expect that Neo-Adjuvant Abemaciclib with Fulvestrant with achieve a response rate, greater antiproliferative effect as measured by the Ki-67 index and perhaps improve Breast conservation surgery too.

